## **5.0 SCHEDULED ASSESSMENTS**

### **5.1 Screening (Visit 1) and Baseline (Visit 2) Assessments**

The screening assessment (Visit 1) will occur within 3 months of the first training session. The baseline assessment (Visit 2) will occur within one week of the first training following commencement of the study. These assessments will include the following tests or procedures:

1. Documentation of demographic information, including gender, age, allergies, and current medications (screening visit 1).
2. Clinical examination of the ears (screening and baseline visit 1 and 2).
3. Documentation of key clinical data such as confirmation of thresholds being  $\leq 25$  dB HL up to 4 kHz,  $\leq 30$  dB HL at 4 kHz, and  $\leq 45$  dB HL at 6 and 8 kHz, and the absence of any ear disorder (screening visit 1).
4. Blood draw for laboratory testing that include a serum pregnancy test\*, electrolyte panel, BUN, Cr, ALT, and AST and DNA analysis will be collected (baseline visit 2).

\*Women capable of becoming pregnant will be asked to have a pregnancy test before beginning this study. Women capable of becoming pregnant will be instructed to use effective birth control methods and not to become pregnant while participating in this study as there may be unknown risks to the unborn child. There may be long-term effects of the treatment being studied that could increase the risk of harm to an unborn child. The study team must be notified if the birth control method fails while on the study and/or if the participant becomes pregnant while participating in this research study.

5. Audiogram, ECochG, DPOAE, and WIN testing to document baseline measurements (baseline visit 2).

**Audiometry:** The audiogram will be performed to look for TTS and PTS. Earphones will be placed over the participant's ears and a series of tones at a soft volume will be played at varying frequencies. The participant indicates that they hear the tones by pressing a button. Thresholds will be measured from .025-16 kHz. If there is an absence of a threshold at the limits of the equipment, the threshold will be reported as equipment limits (in dB HL) + 10 dB HL. As with the DPOAE, all equipment and procedures are based on a clinically approved protocol. Each ear will be tested separately.

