### **5.4 Follow-Up Assessments (Visits 3, 4 and 5)**

The follow-up assessments will occur after training and include the following tests or procedures:

1. Audiogram and DPOAEs to measure for TTS and auditory changes, as soon as possible after the training session. The exact time of testing following training operations will be documented. A clinical ear exam will be completed prior to the audiogram and DPOAEs. (follow-up visit 3 and 5).
2. Baseline environmental/ambient sound measurements will be recorded at the start of each test session, including the peak ambient noise level and the average noise level (follow-up visit 3 and 5).
3. Collection of blood for laboratory testing to include an electrolyte panel, BUN, Cr, ALT, and AST. This will occur within 12-24 hours following drug intake (follow-up visit 4).
4. Cognitive assessments within 24 hours following drug intake, including (follow-up visit 4):
  - a. Digit-symbol substitution test (processing speed)
  - b. Verbal fluency (working memory, speech/language)
  - c. Stroop (Executive function, inhibition)
  - d. List Learning task/RBANS (memory)

Additionally, after each officer is asked about potential study-related side effects for safety monitoring, they will be asked a question regarding their feeling of safety on the job, i.e. they will be asked *“if they feel safe partaking in required responsibilities associated with their job at this time or not?”*

5. Completion of LENS-Q 1-minute noise screening for noise exposure questionnaire (follow-up visit 5).
6. Audiogram, ECochG, DPOAE, and WIN testing 30 days (+/- 3 days) after each training session to assess for PTS and auditory changes, only if TTS is observed from #1 (visit 5).
7. Documentation of adverse events at all follow-up visits (5-30 minutes post, within 24 hours and at 30 day visit) (follow-up visit 3, 4 and 5).

Follow-up assessments will be planned at the stated time points; actual follow up times may vary due to patient logistics and compliance.

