1 PURPOSE

This document describes the planned statistical strategies for the analysis of data for the “Pharmaceutical Interventions for Noise-Induced Hearing Loss–Acute Exposure Treatment (PINIHL-AET)” Study. The document will be shared with the members of the Data Safety Monitoring Board (DSMB) and will be modified based on their feedback and requests.

Data reports will be prepared for the DSMB and will be part of the DSM report that will be prepared by the study team with assistance from the study statistician. The DSM report will be prepared for the DSMB semi-annually and at other times at the discretion of the DSMB. The DSM report will be reviewed by the DSMB, and will be submitted to the PI. The DSMB must meet at least every six months beginning six months after study activation at Washington University beginning six months after enrollment of the first patient at the secondary site, or due to Adverse Events (AE) or Serious Adverse Events (SAEs) to ensure subject safety through data, process or conduct of study and recommend to the sponsor on continuation, modification, or termination of the study, and no more than one month prior to the due date of the DSM report to the PI.

In the event of future amendments to the protocol, this SAP will be modified as necessary to account for changes relevant to the statistical analysis.

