5 GENERAL ASPECTS FOR STATISTICAL ANALYSES

5.1 General Methods

- All analyses and summaries will be produced using SAS® version 9.4 (or higher).
- Standard descriptive statistics will be used to describe distribution of demographic, clinical, and audiometric characteristics as well as outcome measures for all the study samples listed in section 2.5. For continuous level characteristics Q-Q plots and Shapiro-Wilk test will be used to test assumption of normality. If continuous level data is found to be normally distributed data, mean and standard deviation will be used as descriptive statistics, and if the assumption of normality is violated, we will report median and range for description of these variables. Frequency and relative frequency will be used for description of categorical level variables.
- The same number of decimal places as in the raw data will be presented when reporting range, 1 more decimal place than in the raw data will be presented when reporting the mean and median, and 2 more decimal places than in the raw data will be presented when reporting the standard deviation.
- Unless stated otherwise, tabular summaries will present columns for the active treatment arm (“ZNS (100 mg PO)”), placebo arm, and overall.
- Unless stated otherwise, the relative frequency will be based on the number of non-missing observations. The column header will still contain the number of subjects in the treatment group. There will be a row for the number of non-missing observations in the table (at each time point, if required) for each variable being summarized.
- Any calculated p-values will be presented to 3 decimal places; p-values less than 0.001 will be presented as ‘p<0.001’ and p-values greater than 0.999 will be presented as ‘p>0.999’.
- All relevant subjects data will be included in listings and sorted by treatment group, Participant ID, and visit, as applicable, for all randomized subjects.
- Unscheduled or repeat assessments will not be included in summary tables unless specified. All assessments will be included in the participant listings.
- All tables, listings and figures will include footers that identify the name of the program that created the output, together with the date and time on which it was created. Headers will include the total number of pages that the presentation contains and, for each page, the number of the page within the presentation.

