Analysis of variance (ANCOVA) will be used for comparison of outcome measures between each of the ZNS groups and placebo study group after controlling for baseline value, age, pre-op hearing dichotomized to: normal to minimal hearing loss and slight to mild loss, noise exposure history dichotomized to: high risk and low risk, average post-shooting TTS.

Statistical analyses will be conducted using the SAS software (SAS Institute Inc., Cary, N.C.,

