8.1.1 Safety monitoring

Adverse events will be tracked for the UA site at the follow up 14-30 day visit. All adverse events must be recorded on the AE tracking case report form (CRF). AEs related to study medication only will be tracked.

Each officer will be asked about potential study-related side effects for safety monitoring, i.e. they will be asked *“if they had any unpleasant experience, including an illness or other physical event, in the past 4 hours, whether they think it is study related or not?”* This will be followed by a question regarding their feeling of safety on the job, i.e. they will be asked *“if they feel safe partaking in required responsibilities associated with their job at this time or not?”*

Number and percentage of officers self-reporting potential study-related side effects or that report that they do not *feel safe partaking in required responsibilities associated with their job* will be reported to DSMB.

Cognitive assessments will be performed at baseline and within 24 hours following drug intake will be used to assess any side effects of ZNS on cognition. The assessments will be:

- a. Digit-symbol substitution test: Measures processing speed
- b. List learning task/RBANS: Measures memory function.
- c. Verbal fluency test (word finding task): Measures working memory, speech/language
- d. Stroop test: Measures executive functioning (vigilance, attention, inhibition).

Paired samples t-test will be used to explore the change from baseline to 24 hours following drug intake for each of the cognitive assessment instruments. The within subject change will be also compared to clinically meaningful differences for each of the test, to assess whether the observed change is clinically/practically important. Results of this analysis will be presented to DSMB.

The study team will monitor for adverse events on an ongoing basis. Once the team becomes aware of an adverse event, the AE will be reported according to institutional guidelines. Reporting requirements for University of Akron study team may be found in Section 1.1 of protocol. Reporting requirements for secondary site study teams participating in University of Akron-coordinated research may be found in Section 1.2 of protocol.

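### SAP 8.1.1 states no between-arm estimate, test or confidence interval for cognition, so its within-subject methods cannot by themselves attribute a change to ZNS

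*SAP*

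**What the plan says.** - **Aim.** SAP 8.1.1 says that the cognitive tests, given at baseline and within 24 hours of dosing, "will be used to assess any side effects of ZNS on cognition".
- **Methods.** The same section states two: "Paired samples t-test will be used to explore the change from baseline to 24 hours following drug intake" for each instrument, and "The within subject change will be also compared to clinically meaningful differences for each of the test". The results go to the DSMB. It does not say whether the paired test is run by arm or on all subjects, and it gives no values for the meaningful differences.
- **Schedule.** Protocol 5.1 and 5.4 list the same four tests (digit-symbol substitution, list learning/RBANS, verbal fluency, Stroop) at Visit 2 and Visit 4. "The baseline assessment (Visit 2) will occur within one week of the first training", and Visit 4 falls within 24 hours of the dose.
- **Elsewhere.** Protocol 12 contains no cognitive analysis. The table, listing and figure indexes in SAP 12.1 to 12.3 contain no cognitive output.
- **Default layout.** SAP 5.1: "Unless stated otherwise, tabular summaries will present columns for the active treatment arm", the placebo arm and all subjects together.
- **A between-arm model already in the SAP.** For the audiologic secondary outcomes, SAP 7.1.2 plans an ANCOVA that "will be used for comparison of outcome measures between each of the ZNS groups and placebo study group after controlling for baseline value".

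**The concern.** Whether ZNS impairs cognition is a causal question about the drug. A change from baseline to 24 hours contains the drug effect plus everything else that moves scores between the two visits. Two candidates are practice on a repeated test and fatigue after a day of range training. For an officer dosed after the first training, the retest comes about eight days or less after baseline (up to seven days, plus one).

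Both kinds of error matter to a DSMB. A practice gain in both arms can hide a decline on ZNS, and a general post-training decline can look like a drug effect. Difficulty with memory or concentration and somnolence are on the protocol's own side-effect list, and the participants are armed officers. The randomized placebo arm is tested on the same schedule, so the data that separate the two explanations will already be in hand.

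**Working it through.** The plan gives no power, SD, practice gain or drug effect for cognition, so there is no figure to reproduce. What follows is an illustration under assumed values.

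**Inputs.** From the documents: 66 per arm in full (SAP 2.7), 22 per arm at the interim (SAP 9), about 34 officers a year (Protocol 12.4). Assumed: normal change scores with SD 1, higher is better, mean g on placebo and g + d on ZNS. Here g is change shared by both arms and d is the drug effect. A flag is a two-sided 0.05 result in the direction of decline.

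**What each method estimates.**
- Paired test, all subjects: g + d/2.
- Paired test, ZNS arm: g + d.
- Between-arm difference in change: (g + d) - g = d.

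Only the last is free of g.

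**Probability of a flag.** ZNS arm: noncentral t with n - 1 df and noncentrality (g + d)√n. Between-arm: 2n - 2 df and noncentrality d√(n/2). All subjects: simulation (60,000 to 100,000 runs per setting), because the pooled changes mix two means. Worked case with d = -0.5, n = 66, g = 0.4: the ZNS-arm noncentrality is -0.1 × 8.12 = -0.81, giving 0.12. The between-arm noncentrality is -0.5 × 5.74 = -2.87, giving 0.81.

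| d, n per arm | Method | g = 0 | 0.1 | 0.2 | 0.4 |
|---|---|---|---|---|---|
| -0.5, 66 | paired, all | 0.80 | 0.38 | 0.07 | 0.00 |
| | paired, ZNS | 0.98 | 0.89 | 0.67 | 0.12 |
| | between-arm | 0.81 | 0.81 | 0.81 | 0.81 |
| -0.5, 22 | paired, all | 0.34 | 0.15 | 0.05 | 0.00 |
| | paired, ZNS | 0.61 | 0.43 | 0.27 | 0.07 |
| | between-arm | 0.37 | 0.37 | 0.37 | 0.37 |
| -0.8, 22 | paired, all | 0.68 | 0.43 | 0.21 | 0.02 |
| | paired, ZNS | 0.95 | 0.88 | 0.76 | 0.43 |
| | between-arm | 0.74 | 0.74 | 0.74 | 0.74 |
| -0.8, 66 | paired, all | 0.99 | 0.90 | 0.57 | 0.02 |
| | paired, ZNS | 1.00 | 1.00 | 1.00 | 0.89 |
| | between-arm | 0.995 | 0.995 | 0.995 | 0.995 |

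The ZNS-arm paired test flags more often than the between-arm test in 10 of these 16 settings, all with a small or moderate shared gain.

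**No drug effect, shared decline, 22 per arm.**

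| Shared decline | paired, all | paired, ZNS | between-arm |
|---|---|---|---|
| 0.2 SD | 0.25 | 0.14 | 0.025 |
| 0.4 SD | 0.74 | 0.43 | 0.025 |

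Reading two paired tests side by side does not cure this. With independent arms, a significant decline on ZNS but not on placebo has probability 0.144 × (1 - 0.144) = 0.12 at a shared decline of 0.2 SD, and 0.433 × (1 - 0.433) = 0.25 at 0.4 SD.

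**Precision of the between-arm difference.** The 95% half-width is t(0.975, 2n - 2) × √(2/n). Half a year at 34 officers a year is 17 officers, or 8 to 9 per arm.

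| n per arm | 8 | 9 | 17 | 22 | 34 | 66 |
|---|---|---|---|---|---|---|
| Half-width (SD) | 1.07 | 1.00 | 0.70 | 0.61 | 0.48 | 0.34 |

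**The case against.** The strongest reply is that this is exploratory safety monitoring, which SAP 8.1.1 says in so many words. Comparing each officer's change with a meaningful difference is a legitimate individual screen whatever the arm, and the job-safety question addresses fitness for duty directly. For a screen, sensitivity matters, and the ZNS-arm paired test is often the more sensitive. The documents give no practice gain and do not say whether alternate test forms are used, so the shared change could be small. Early on, a between-arm interval tells the DSMB little. All of this stands. It limits the point to an improvement and argues for keeping the paired results.

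A reader might go further and infer that the SAP ignores the placebo arm. The text does not support that. SAP 8 uses the Safety Sample Set, which SAP 4.3 defines to include placebo recipients. The SAP 5.1 default would put placebo change beside ZNS change in any cognitive table. What is missing is a formal estimate, test or interval.

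A reader might also infer from the blinded table shells in SAP 2.5 that the DSMB is kept from by-arm safety data. That is not established. The content of the DSMB shells is agreed in documents not seen here, and SAP 2.5 lets members request unblinded data when they find a safety issue. The early stopping rule in SAP 8.1.1 lets the DSMB break the blind after a serious event. SAP 1 allows for meetings "or due to Adverse Events (AE) or Serious Adverse Events (SAEs) to ensure subject safety" and for changing the SAP at the DSMB's request. No change to DSMB reporting is proposed.

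**Conclusion.** The point holds as a cheap improvement. The stated aim is to assess an effect of ZNS, but the stated methods estimate the drug effect mixed with any change common to both arms, and no between-arm result is planned for cognition in either document. Descriptive columns by arm, if produced, do not resolve this.

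The size cannot be taken from the documents. Under the assumed values, the chance of flagging a true decline of 0.5 SD at 66 per arm ranges from 0.98 down to 0.12 with the ZNS-arm paired test, and from 0.80 to 0.00 with all subjects, as the shared gain goes from 0 to 0.4 SD. The between-arm test stays at 0.81. With no drug effect and a shared decline of 0.4 SD at 22 per arm, the false-flag rates are 0.43, 0.74 and 0.025 respectively. The benefit is attribution rather than a general gain in power, and the estimate is useful mainly later in the trial. The primary efficacy result is unaffected.

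**What to change.** In SAP 8.1.1, after the sentence on the paired t-test, add:

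> For each instrument the 24-hour score is also compared between ZNS and placebo by ANCOVA adjusted for the baseline score, and the ZNS minus placebo difference is reported with its 95% CI.

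Keep the paired results and the within-subject comparison as description, shown by arm. Add one cognitive table to SAP 12.1.

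The cost is one sentence, four extra models (one per instrument) and one table. No new visits, participants or data are needed. The four intervals carry no multiplicity correction and need cautious reading. At the first DSMB reviews they will be wide, about 1.0 to 1.1 SD either side of the estimate at 8 to 9 per arm.

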8.2 Clinical Laboratory Tests

Biochemistry blood tests will be performed at screening for all subjects.

The following biochemistry laboratory parameters will be measured: Chloride, sodium, potassium, Carbon dioxide, Blood urea Nitrogen (BUN), creatinine, Alanine aminotransferase (ALT), Aspartate aminotransferase (AST).

Laboratory test results will be summarized descriptively by treatment group using Safety Analysis Sample.

All clinical laboratory results will be listed. Laboratory values that are outside the normal range will be flagged.

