## **5.5 Blood collection, transportation, and storage**

Blood samples will be collected from each participant during the baseline visit and the post-training visit within 24 hours. A phlebotomist will draw blood into a red-top tube (EDTA or citrate). Samples will be labeled with a study identification number. Samples to be used for safety labs will be sent to the lab by the phlebotomist. PGx samples will be stored in a 2-8°C degree refrigerator or a -

20°C degree freezer at Akron. Samples will then be transported for extraction and stored in a -80°C freezer at Gateway Biotechnology's lab.

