12 APPENDICES

12.1 Index of Proposed Tables

Table Number	Table Title	Sample Set
Table 14.1.1	Subject Disposition	ITT Sample Set
Table 14.1.2	Protocol Deviation	Safety Sample Set
Table 14.1.3	Demographic and Baseline Characteristics	Safety Sample Set
Table 14.1.4	Medical and Surgical History	Safety Sample Set
Table 14.1.5	Concomitant Medications	Safety Sample Set
Table 14.1.6	Study Dose Administration	Safety Sample Set
Table 14.2.1.1	Primary Efficacy Analysis: Permanent Threshold Shift (PTS) in the Contralateral Ear Using Audiogram	ITT Sample Set
Table 14.2.1.2	Primary Efficacy Analysis: Permanent Threshold Shift (PTS) in the Contralateral Ear Using Audiogram	PP Sample Set
Table 14.2.1.3	Sensitivity Analysis 1: Permanent Threshold Shift (PTS) in at least one of the ears Using Audiogram	ITT Sample Set
Table 14.2.1.4	Sensitivity Analysis 1: Permanent Threshold Shift (PTS) in the Contralateral Ear Using Audiogram	PP Sample Set
Table 14.2.1.5	Sensitivity Analysis 2: Permanent Threshold Shift (PTS) Using Audiogram	ITT Sample Set
Table 14.2.1.6	Sensitivity Analysis 2: Permanent Threshold Shift (PTS) Using Audiogram	PP Sample Set
Table 14.2.1.7	Audiogram Results on Hearing Thresholds: Actual and Change from Baseline	ITT Sample Set
Table 14.2.1.8	Audiogram Results on Hearing Thresholds: Actual and Change from Baseline	PP Sample Set
Table 14.2.2.1	DPOAE OAE Amplitude: Actual and Change from Baseline	ITT Sample Set
Table 14.2.2.2	DPOAE OAE Amplitude: Actual and Change from Baseline	PP Sample Set
Table 14.2.2.3	DPOAE Noise Floor: Actual and Change from Baseline	ITT Sample Set
Table 14.2.2.4	DPOAE Noise Floor: Actual and Change from Baseline	PP Sample Set
Table 14.2.3.1	ECochG Results: Actual and Change from Baseline	ITT Sample Set
Table 14.2.3.2	ECochG Results: Actual and Change from Baseline	PP Sample Set
Table 14.2.4.1	WIN Test: Actual and Change from Baseline	ITT Sample Set
Table 14.2.4.2	WIN Test: Actual and Change from Baseline	PP Sample Set
Table 14.3.1.1	Overall Summary Adverse Events	Safety Sample Set
Table 14.3.1.2	Summary of Treatment-Emergent Adverse Events by System Organ Class and Preferred Term	Safety Sample Set

Table Number	Table Title	Sample Set
Table 14.3.1.3	Summary of Serious Treatment Emergent Adverse Events	Safety Sample Set
Table 14.3.1.4	Summary of TEAEs by severity using the Common Terminology Criteria for Adverse Events (CTCAE grades) by Maximum-reported Severity	Safety Sample Set

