Table 14.3.1.5	Summary of Related Treatment Emergent Adverse Events	Safety Sample Set
Table 14.3.1.6	Summary of TEAEs Leading to Study Drug Interruption	Safety Sample Set
Table 14.3.1.7	Summary of TEAEs Leading to Study Drug Withdrawn	Safety Sample Set
Table 14.3.2	Summary of Biochemistry Lab Results at Screening	Safety Sample Set

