12.2 Index of Proposed Listings

Listing Number	Listing Title	Sample Set
Listing 14.3.3.1	Overall Summary of Physical Examination of Ears Results at Screening	Safety Sample Set
Listing 16.1.1	Subject Enrollment and Disposition	All Subjects
Listing 16.1.2.1	Subject Inclusion and Exclusion Criteria	All Subjects
Listing 16.1.2.2	Protocol Deviations	All Subjects
Listing 16.1.3	Demographic Characteristics	All Subjects
Listing 16.1.4	Medical and Surgical History	Safety Sample Set
Listing 16.1.5	Hearing History and Occupation Exposure	Safety Sample Set
Listing 16.1.6	Concomitant Medications	Safety Sample Set
Listing 16.1.7	Study Drug Administration	Safety Sample Set
Listing 16.2.1	Audiogram Results on Hearing Thresholds	ITT Sample Set
Listing 16.2.2	Distortion Product Otoacoustic Emissions (DPOAE) Results	ITT Sample Set
Listing 16.2.3	Electrocochleography (ECochG) Results	ITT Sample Set
Listing 16.2.4	Word in Noise (WIN) Test Results	ITT Sample Set
Listing 16.2.5	LENS-Q Non-Military Occupational Noise Exposure Results	ITT Sample Set
Listing 16.2.6	LENS-Q Military Occupational Noise Exposure Results	ITT Sample Set
Listing 16.2.7	LENS-Q Non-Military Occupational Chemicals Exposure Results	ITT Sample Set
Listing 16.2.8	LENS-Q Military Occupational Chemicals Exposure Results	ITT Sample Set
Listing 16.2.9	LENS-Q Non-Occupational/Recreation Noise Exposure Results	ITT Sample Set

Listing Number	Listing Title	Sample Set
Listing 16.2.10	LENS-Q NON-Occupational/Recreation Chemicals Exposure Results	ITT Sample Set
Listing 16.2.11	Noise Exposure Questionnaire (NEQ) Responses	ITT Sample Set
Listing 16.2.12	Tinnitus Functional Index (TFI) Questionnaire Responses	ITT Sample Set
Listing 16.2.13	Audiologic and Medical History Questionnaire Responses	ITT Sample Set
Listing 16.2.14	Hearing Handicap Inventory for Adults (HHIA-A) Questionnaire Responses	ITT Sample Set
Listing 16.3.1.1	Serious Adverse Events	Safety Sample Set
Listing 16.3.1.2	Adverse Events Resulting in Death	Safety Sample Set
Listing 16.3.1.3	Treatment-emergent Adverse Events	Safety Sample Set
Listing 16.3.1.4	Treatment-emergent Adverse Events leading to Study Drug Interruption	Safety Sample Set
Listing 16.3.1.5	Treatment-emergent Adverse Events leading to Study Drug Withdrawn	Safety Sample Set
Listing 16.3.2.1	Clinical Laboratory Results at Screening: Biochemistry	Safety Sample Set
Listing 16.3.2.2	Pregnancy Test at Screening	Safety Sample Set

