12.3 Index of Proposed Figures

Figure Number	Figure Title	Sample Set
Figure 14.1.1	QQ Plot for Age	Safety Sample Set
Figure 14.1.2	QQ Plot for Biochemistry Lab Parameters	Safety Sample Set
Figure 14.1.3	QQ Plot for ECG Parameters	Safety Sample Set
Figure 14.2.1	QQ Plot for Distortion Product Otoacoustic Emissions (DPOAE) OAE Amplitude	ITT Sample Set
Figure 14.2.2	QQ Plot for Distortion Product Otoacoustic Emissions (DPOAE) Noise Floor Amplitude	ITT Sample Set
Figure 14.2.3	QQ Plot for Electrocochleography (ECochG)Parameters	ITT Sample Set
Figure 14.2.4	QQ Plot for Word in Noise (WIN) Test Parameters	ITT Sample Set

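### The SAP times biochemistry at screening, but chemistry is drawn only at Visit 2 and post-dose Visit 4, so as indexed the post-dose draw has no summary by arm

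*SAP*

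**What the plan says.** SAP 8.2 gives one time point for chemistry: "Biochemistry blood tests will be performed at screening for all subjects". It names eight analytes (chloride, sodium, potassium, carbon dioxide, BUN, creatinine, ALT, AST). It then promises a descriptive summary by treatment group on the safety sample, a listing of all results, and flags for values outside the normal range. The summary sentence names no visit.

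The SAP indexes hold three chemistry outputs:

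- Table 14.3.2, "Summary of Biochemistry Lab Results at Screening"
- Listing 16.3.2.1, "Clinical Laboratory Results at Screening: Biochemistry"
- Figure 14.1.2, "QQ Plot for Biochemistry Lab Parameters"

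The protocol schedules the draws differently. Section 5.1, item 4, places the first panel at baseline: "electrolyte panel, BUN, Cr, ALT, and AST and DNA analysis will be collected (baseline visit 2". Section 5.4, item 3, places the second after the dose: "This will occur within 12-24 hours following drug intake (follow-up visit 4". Section 5.5 confirms the pair: "Blood samples will be collected from each participant during the baseline visit and the post-training visit within 24 hours". The calendars in protocol 9.0 and SAP 2.6 both mark the blood draw at Visits 2 and 4 and leave Visit 1 blank.

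**The concern.** The SAP's laboratory section, its one laboratory table and its one chemistry listing all name a visit at which no blood is taken. Programmed literally, the table would have nothing to report. If screening is read loosely as the pre-dose baseline, the table has data but stops before the drug is given.

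Visit 4 is the only chemistry draw after dosing, so it alone can show whether the single dose moves any analyte. Metabolic acidosis is among the serious risks listed for zonisamide (SAP 3.5; protocol 7.1.7, which calls serious effects rare), and carbon dioxide is in the panel. Without a summary by arm, a modest shift between arms would have to be found by reading a listing line by line. What is at stake is the readability of the safety report, not the efficacy conclusion.

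**Working it through.** There is no formula to reproduce. The check compares the visit named for chemistry in each place and then counts the indexed outputs.

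**Step 1: where chemistry is placed**

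| Source | Visit 1 (screening) | Visit 2 (baseline) | Visit 4 (post-dose) |
|---|---|---|---|
| Protocol 5.1, item 4 | no | yes | – |
| Protocol 5.4, item 3 | – | – | yes, 12-24 h after the dose |
| Protocol 5.5 | no | yes | yes |
| Protocol 9.0 calendar | no | yes | yes |
| SAP 2.6 calendar | no | yes | yes |
| SAP 8.2 | named | not named | not named |
| SAP Table 14.3.2, Listing 16.3.2.1 | named | not named | not named |

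Scheduled chemistry draws: 2, with 0 at screening. SAP 8.2 therefore conflicts with SAP 2.6 as well as with the protocol.

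**Step 2: whether screening could simply mean baseline**

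The SAP separates the terms. Its calendar has one column for Visit 1 as screening and another for Visit 2 as baseline, and SAP 8.1.1 uses baseline for the cognitive tests, which are also done at Visits 2 and 4. Granting the loose reading would repair the pre-dose half only.

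**Step 3: what the indexes contain**

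- Tables in SAP 12.1: 6 (14.1.x) + 8 (14.2.1.x) + 4 (14.2.2.x) + 2 (14.2.3.x) + 2 (14.2.4.x) + 7 (14.3.1.x) + 1 (14.3.2) = 30. One of the 30 is a laboratory table.
- Chemistry outputs: 1 table + 1 listing + 1 figure = 3. Two name screening, one (the QQ plot, a normality check) names no visit, and 0 name Visit 4.
- Tables titled in the style of "ECochG Results: Actual and Change from Baseline": 2 (14.2.1.7-8) + 4 (14.2.2.1-4) + 2 (14.2.3.1-2) + 2 (14.2.4.1-2) = 10, all efficacy. The two-visit format is thus already in use, although its absence for chemistry is not in itself an error.

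**Step 4: how much data this concerns**

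Assuming that all 132 planned officers are dosed and attend Visit 4, there would be 132 × 8 = 1,056 post-dose values. With 66 per arm, that is 66 × 8 = 528 in each. All would be listed; as indexed, none is in a table by arm. Missed draws would lower these counts without changing the point.

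**The case against.** The strongest reply is that the summary sentence in SAP 8.2 has no visit restriction, whereas SAP 8.3 expressly limits its summary of ear examinations to the screening visit. When the authors wanted a screening-only summary they said so. On that reading a Visit 4 summary by arm is already promised, and only the titles are too narrow.

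The index is also weak evidence of what will be produced. It is headed as proposed, and it gives no table of its own to analyses planned in the text, such as the cognitive change analysis in 8.1.1 or the supportive logistic regression in 7.1.1. It carries apparent leftovers too, among them contralateral-ear titles and ECG outputs. Later steps offer further chances of correction: specifications are reviewed after the SAP is final (11.1), validation refers to the protocol as well as the SAP (11.2), and the DSMB's table shells are agreed separately (2.5).

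Much of this stands. A reader might infer that no summary of post-dose chemistry is planned at all, or that the Visit 4 results would go unreported. The documents support neither. The unrestricted summary sentence points the other way. All results are listed and flagged, SAP 5.1 puts all assessments in the listings, and SAP 10.1.5.3 sorts listings by arm and visit.

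The contradiction itself is not removed. Screening is the only time point that 8.2 names, and it is wrong. The one table that would carry out the general promise repeats it. Specifications are built from the SAP, so independent double programming to one specification could reproduce the wrong visit twice. Change columns and out-of-range counts are a different matter: nothing in 8.2 requires them, so they are an improvement, not part of the error.

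**Conclusion.** The concern holds for the visit named in SAP 8.2, Table 14.3.2 and Listing 16.3.2.1. It is wrong as written: there are 0 chemistry draws at screening, against 2 scheduled elsewhere. As indexed, the sole post-dose draw has no summary by arm for any of the 8 analytes.

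This rests on reading the table titles at face value. If the general sentence in 8.2 is applied to every scheduled visit, the intended summary exists and the defect reduces to the stated time point and the titles. The correction is the same either way. The documents do not say how likely one 100 mg dose is to shift chemistry, so no safety signal is claimed to have been missed. The primary endpoint, power and alpha are unaffected.

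**What to change.** **Correct what is wrong as written.** In SAP 8.2, replace the screening time point with: at baseline (Visit 2) and 12-24 hours after dosing (Visit 4). Retitle Table 14.3.2 and Listing 16.3.2.1 to match, and have the table summarise both visits by arm for all eight analytes.

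**Cheap addition.** Show change from Visit 2, and counts of out-of-range values at each visit, by arm in the same table. The title pattern of the existing efficacy tables can be reused.

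**Cost.** The correction takes one sentence in SAP 8.2, one table shell and one listing title; the addition takes a few more table columns. Both draws are already scheduled, so no new data are collected. SAP 11.1 has output specifications written after the SAP is final, so correcting the SAP first carries the right visits into them.
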